## **I. Purpose, Background and Rationale**

### **A. Aim and Hypotheses**

Migraine is a common, disabling neurological disorder, affecting 10–12% of US population; 18% women and 6% men. [1]. The treatment of migraine headache includes preventive therapies and abortive therapies. There are several preventive therapies available with the goal to decrease the overall frequency and intensity of migraine attacks. The abortive medications are used during acute migraine episode. There are several medications like NSAIDs, triptans etc. that are used for migraine abortion.

Despite of the various migraine abortive therapies available, there is an ongoing need for novel therapies. Beta-blocker medications have been used for migraine prevention for a long time. However, their use for migraine abortion has not been well identified. In this study, we propose the use of topical beta-blocker eye drops for acute treatment of migraine headache. If successful beta-blocker eye drops will be a simple, painless and low cost acute treatment of migraine.

### **Specific aims**

- 1) To assess the efficacy (headache freedom at 2 hours) of Timolol 0.5% ophthalmic solution compared to placebo in acute treatment of migraine headache.
- 2) To assess the safety and tolerability of Timolol 0.5% ophthalmic solution in treatment of acute migraine headache.

### **Hypothesis:**

Oral beta-blockers are a class of medications frequently used to control blood pressure, angina, and heart irregularities. Certain oral beta-blockers such as propranolol and timolol are used on a daily basis to prevent migraines. However, propranolol and timolol tablets have not been shown to be effective as an acute treatment to stop attacks of migraine because of their longer onset of action. We propose that, since beta-blocker eye drops, unlike tablets are quickly absorbed through the covering of the eye and lining of the nose and can be detected in the bloodstream within minutes, can be beneficial and efficacious in the treatment of headache abortion.

Timolol is a non-selective beta-adrenoreceptor antagonist [7]. Oral timolol (20-30 mg daily) has been studied in 3 randomized controlled trials and have been found to reduce headache frequency by more than 50% when compared to placebo.[8-10] It has been approved by FDA for prophylactic use in migraine patients and had level A evidence to support this indication. The prophylactic benefit of beta-blockers in migraine treatment is not completely understood. It may be related to the effect of beta-blockers on central autonomic vascular tone center, which in turn modulate the cerebrovascular reactivity to sensory stimulation.[11] [12] Propranolol, a beta-adrenergic blocker modulates serotonergic transmission, regulates periaqueductal pathway activation and prevents central sensitization, normalizes neuronal excitability in the CNS, and blocks cortical spreading depression (CSD). Topical ocular beta blockers have been reported to be successful in retinal arteriolar spasm,

retinal migraines causing visual field defects, migraines causing oculomotor nerve palsy[14], and as abortive agents in migraine patients[4-6]. Topical timolol maleate solution 0.5% reaches a concentration of 0.5 ng/ml in the plasma within 4 hours of first dose after being used twice daily for 7 days [4].

Topical beta-blockers so far have been noted to be effective for acute migraine episodes only in case reports [4, 5] and a recent case series of 7 patients. [6] To date there have been several case studies of patients successfully using a beta blocker eye drop containing timolol to treat attacks of migraine, however, there have been no randomized controlled trials. We believe that this pilot study, to evaluate the efficacy and safety of a timolol eye drop for acute treatment of migraine headaches, will open doors for future trials and larger studies. If successful, this will be able establish the use of beta-blocker eye drops which is a simple, painless and low cost acute treatment of migraine.

To date, there have been several case studies of patients successfully using a beta-blocker eye drop containing timolol to treat attacks of migraine; however, there have been no randomized controlled trials. The aim of this study is to determine the efficacy of timolol eye drops for the acute treatment of migraine.

## **B. Background and Significance**

### 1. Study Significance:

Migraine and other benign recurrent headache disorders are a major public health problem, particularly among reproductive-aged women. They are associated with substantial personal suffering, disability, and societal expense. The impact of migraine is substantial because of its high prevalence, accompanying significant disability, and risk for other comorbidities. Data from the National Ambulatory Medical Care Survey (NAMCS), and the National Hospital Ambulatory Medical Care Survey (NHAMCS) indicate that headache is among the top 20 reasons for outpatient medical visits and among the top 5 reasons for ED visits. Several preventive and abortive medications are available for the treatment of migraine headaches. Despite of various treatments available, there seem to be an ongoing need for novel therapies.

It is known that ocular symptoms are commonly seen in classic migraine. Retinal spasm or elevated intra-ocular pressure may play a role in causing headaches for some patients. Perimetry study in migraine patients (compared to controls) have shown temporal visual field dysfunction in migraine subjects similar to early stages of glaucoma.[2] Migraine patients may also have retinal ischemic changes and optic nerve ischemia.[3] Topical beta-blockers so far have been noted to be effective for acute migraine episodes only in case reports [4, 5] and a recent case series of 7 patients. [6] The aim of this study is to evaluate the role of topical timolol 0.5% to treat acute migraine attacks and compare the efficacy and tolerability of this product with a topical placebo.

## **C. Rationale**

1. Certain beta-blockers medications like propranolol and timolol have been used as a preventive therapy for migraine headaches. Their safety and efficacy in the prevention of migraines has been well established. In this study we propose the use of topical beta-blocker eye drops for acute treatment of migraine attack. Since topical and local application beta-blocker eye drops are directly absorbed through the ophthalmic and nasolacrimal mucosa and enters the blood stream within minutes.
2. To date, there have been several case studies of patients successfully using a beta-blocker eye drop containing timolol to treat attacks of migraine; however, there have been no randomized controlled trials. The aim of this study is to determine the efficacy of timolol eye drops for the acute treatment of migraine
3. We believe that this pilot study, to evaluate the efficacy and safety of a timolol eye drop for acute treatment of migraine headaches, will open doors for future trials and larger studies. If successful, this will be able establish the use of beta-blocker eye drops which is a simple, painless and low cost acute treatment of migraine.

## **II. Research Plan and Design**

### **A. Study Objectives:**

A. The objective of this study is to assess the efficacy and response to treatment of acute migraines with timolol 0.5% eye drops as compared to placebo.

We will also assess the safety and tolerability of timolol eye drops in acute treatment of migraine headaches using patient satisfaction scale.

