**Table 1: Schedule of events**

Procedure	Baseline Visit	Interim Visit	End of Study Visit
Consent	X		
Demographics	X		
Medical History	X		
Concomitant Medications	X	X	X
Physical Exam	X		X
Vital signs	X		X
Urine pregnancy screen	X		X
Drug Dispensing	X	X	
Drug Accountability		X	X
Adverse events		X	X
Pain Questionnaire	X	X	X
Satisfaction Questionnaire	X	X	X
Data Entry	X	X	X

At any point, during the treatment of their migraine attacks with the study medications, rescue medications (like NSAIDs, triptans or their usual migraine abortive medications) can be taken 120 minutes after the study drug dose, if necessary. After treating their second migraine attack, the subjects will return for an end-of-study visit. This should occur within 7 days after treating their last qualifying migraine, or after 8 weeks of enrolling in the study (whichever comes first). The subject's diary information will be reviewed and all end-of-study visit procedures will be performed

Subjects will use a diary to collect all attack and safety data needed for data analysis. They will use the comparative pain scale to grade their migraine pain level before and at 2 hour after administration of study ophthalmic drops. They will be provided forms during each visit to record their pain score and treatment satisfaction. A safety monitor will be appointed and all adverse reactions will be reported, although we do not anticipate any adverse events given the short duration of the study and established safety of the drug. All data collected from the patients will be entered on a secured spreadsheet/ database. No patient identifiers will be used. Descriptive statistics will establish baseline characteristics and adverse event frequency. Data for the primary endpoint will be statistically analyzed via 2-tailed t-test. Data for the secondary outcome measures will be statistically analyzed for both within and between group changes via 2-tailed repeated measures ANOVA and or independent or dependent t-tests as appropriate. All ANOVAs will be followed by univariate post-hoc tests.

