**H. Collaboration (with another institution, if applicable):**

**I. Single IRB Review for a Multi-site study (if applicable)**

1. For which sites will KUMC serve as the IRB of record?  
Neurology clinics located at Landon Center of Aging, [name]; Indian Creek Neurology Clinic located at [name] and the Spine Center Neurology Clinic located at [name]
2. Indicate which study activities will occur at each site. If all study procedures will be identical across study sites, state this.  
Subjects who meet all inclusion and exclusion criterion will be identified and recruited through routine office visits at each of the above sites. They will be randomized in a double-blinded fashion to either the study medication arm or placebo arm.
3. Describe how you will assess the capacity of each site to perform the research (e.g., expertise, staffing, space, equipment, etc.) If applicable, include site evaluation tools in your IRB submission.  
Since the subjects will be identified and recruited through routine office visits, each of the above sites are fully equipped neurology clinics. The subjects will be identified and enrolled by physicians during the office visits. The clinic rooms, office ancillary staff and equipment will be used just like a regular neurology clinic visit.

4. Describe how the lead investigators will ensure that all participating sites use the IRB-approved version of the protocol, consent, recruitment materials and other study documents.  
We will make sure that all the participating sites and all study investigators are following the IRP protocol. Each site will have the protocol, consent forms, exam forms and other forms (pain scale and patient satisfaction scale).
5. Describe how the lead investigators will communicate with and disseminate new information to other sites (e.g., training meetings, regularly-scheduled conference calls, notifications, etc.)  
Routine meetings and /or conference calls will be conducted to communicate with all study personnel. Any new data or information pertinent to the study will be discussed during these meetings and phone calls.
6. Describe how the lead investigator will assess protocol compliance, unanticipated problems and adverse events at other sites.  
We do not anticipate any adverse events in this study. A safety monitor will be appointed for any adverse events, if any.

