## **V. Data Analysis and Reporting**

**A. Statistical and Data Analysis:** All data collected from the patients will be entered on a secured spreadsheet/ database. No patient identifiers will be used. Descriptive statistics will establish baseline characteristics and adverse event frequency. Data for the primary endpoint will be statistically analyzed via 2-tailed t-test. Data for the secondary outcome measures will be statistically analyzed for both within and between group changes via 2-tailed repeated measures ANOVA and or independent or dependent t-tests as appropriate. All ANOVAs will be followed by univariate post-hoc tests.

**B. Outcome:** The primary end point of the study is to compare differences in headache severity at 120 minutes between study medication and placebo. A statistically significant pain relief in the study medication arm when compared to the placebo arm will determine success of the study. The secondary end point will be to assess the safety and subject satisfaction with treatment.

**C. Study results to participants:** Once the study results are available, they will be conveyed to the subjects either in person during their regular office visit or via telephone calls

**D. Publication Plan:** We plan to publish the study upon completion and results available.

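### Section II.A names a satisfaction scale as the measure of safety, while the adverse events the plan does collect have no stated breakdown by treatment and no fixed timing after dosing

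*Combined protocol and SAP*

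**What the plan says.** Aim 2, under Specific aims in section I.A, is "To assess the safety and tolerability of Timolol 0.5% ophthalmic solution in treatment of acute migraine headache". Section I.B (Study Significance) adds that tolerability is to be compared with a topical placebo. Section II.A then names the instrument: "We will also assess the safety and tolerability of timolol eye drops in acute treatment of migraine headaches using patient satisfaction scale".

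Other sections describe safety differently.

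- Section V.B: "The secondary end point will be to assess the safety and subject satisfaction with treatment". Safety and satisfaction are separate elements here.
- Table 1 (in II.B, repeated in II.E) has a row "Adverse events" marked at the interim and end-of-study visits. Vital signs and physical examination are marked at baseline and end of study only.
- Section II.B provides for a telephone question about adverse events when bottle 1 is mailed back, and for a diary that is to hold safety data. On forms it says: "They will be provided forms during each visit to record their pain score and treatment satisfaction". Section II.I, item 4, mentions exam forms and "other forms (pain scale and patient satisfaction scale".
- On the end-of-study visit, section II.B says: "This should occur within 7 days after treating their last qualifying migraine, or after 8 weeks of enrolling in the study (whichever comes first".
- Sections II.B, II.C and V.A plan a descriptive frequency of adverse events and do not mention treatment.
- The results note in II.C, item 4, reports pain and satisfaction and is silent on adverse events.

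**The concern.** A satisfaction score records whether the subject was content with the treatment. A subject whose headache eased may be satisfied despite faintness or stinging eyes, and a subject with no relief may be dissatisfied without any harm. If II.A is followed as written, a statement on tolerability could rest on satisfaction alone.

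The adverse-event plan that should carry aim 2 is thin. A pooled frequency cannot separate timolol from placebo, and the delay between dosing and questioning varies between subjects and between bottles. The one post-dose set of vital signs might then be taken as objective reassurance, which its timing does not allow. At stake is whether this pilot passes a sound safety statement to the larger studies it is meant to prepare (sections I.C and II.F).

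**Working it through.** The plan gives no figure for safety. Its 26 subjects come from the efficacy calculation, and this point does not depend on that calculation.

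**1. Which measure is the safety measure?** Section II.A says the satisfaction scale. Table 1, the telephone query and the diary in II.B, and the frequency summary in V.A all say adverse events. Section V.B keeps safety and satisfaction apart. These cannot all stand as the definition of one endpoint, and II.A is the outlier.

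**2. Can adverse events be assigned to a treatment?** Under II.B, one attack is treated per bottle, and bottle 1 must be received before bottle 2 is supplied. Events reported at the interim contact therefore belong to bottle 1. Events reported at end of study belong to bottle 2, or to the interval between the interim contact and use of bottle 2. Most events can be tabulated by treatment. What is missing is a rule for events that start or are reported late, and any statement that the table will be split by treatment. Section II.L, item 1d, on types of analyses, carries no entry. The t-tests and ANOVA named for secondary outcomes suit scores rather than event counts.

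**3. How long after dosing are subjects asked?**
- Bottle 1: no interval is stated between the treated attack and the interim contact.
- Bottle 2: 0 to 7 days, cut short by the 8-week limit. Eight weeks is 8 × 7 = 56 days, so an attack on day 55 leaves 56 − 55 = 1 day. This is an extreme case, but it shows the interval is not fixed.

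**4. What can the post-dose vital signs show?** With 1:1 allocation of 26 (section II.C), 26 / 2 = 13 subjects per sequence.
- Timolol then placebo: about 13 subjects, whose only post-dose set follows placebo.
- Placebo then timolol: about 13 subjects, whose set comes up to 7 days after timolol. The Hypothesis text in I.A expects that the drops "can be detected in the bloodstream within minutes".

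Neither group gives a reading timed to an acute effect. Timing aside, 13 against 13 has 80% power (two-sided 5%, normal approximation) only for a difference of (1.960 + 0.842) × √(2/13) = 1.10 SD.

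**5. What would an exact interval show?** With zero events in n exposures, the upper 95% limit is 1 − 0.05^(1/n) one-sided and 1 − 0.025^(1/n) two-sided. For n = 26 timolol exposures:
- one-sided: 1 − 0.05^(1/26) = 10.9%
- two-sided: 1 − 0.025^(1/26) = 13.2%

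These limits reflect the size of the trial and would hold under perfect capture. They do not measure the defect in II.A, but they show what a by-treatment table would make visible.

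**The case against.** The best defence is that II.A contains one loose phrase and that the working plan lies elsewhere: adverse events at two contacts, a diary for safety data, a frequency summary and monthly review of all data (II.L). This largely stands. A reader might infer that aim 2 cannot be answered, or that no harm data exist at the level of the attack. The documents do not support either inference, because adverse events are sought after each bottle and the order of the bottles links most of them to a treatment.

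A reader might also infer that adverse events are captured by recall alone, because the forms named are mainly for pain and satisfaction. That is not established. Section II.B assigns safety data to the diary, and neither the diary nor the scale appendices are in the text available. Equally, the silence of II.C, item 4, does not show that events went uncollected or unsummarised.

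It is fair to add that the plan nowhere names end-of-study vital signs as a comparison of timolol with placebo. The point about them is therefore a caution on interpretation. Taking vital signs at the interim visit would not help. They too would come at an unfixed time after dosing, and only from subjects who attend in person.

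Three things remain unanswered: the wrong instrument in II.A, the absence of a by-treatment summary although I.B promises a comparison, and the unfixed timing of questioning.

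**Conclusion.** The point holds in this form. Section II.A names a measure that does not capture harm and that conflicts with II.B, Table 1 and V.B. Adverse events are planned after each bottle, but without a stated breakdown by treatment, an attribution rule or a fixed interval from dosing. The single post-dose set of vital signs and examination follows placebo in about 13 of 26 subjects and comes up to 7 days after timolol in the rest, so it cannot show an acute difference between treatments. This should be corrected. It does not touch the primary endpoint, and aim 2 remains answerable to a limited degree.

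The 13/13 split assumes equal sequences and two treated attacks in every subject; a subject with one attack has end-of-study vital signs after bottle 1. The figure of 26 timolol exposures assumes no early withdrawal. Section II.D, item 3, ties withdrawal to an adverse effect of the study drug, whereas II.L ties it to any adverse event. These passages must be reconciled, because either rule would remove the second period for subjects with an event on bottle 1.

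**What to change.** 1. In II.A, replace the closing words that name the satisfaction scale with: *using adverse events recorded for each treated attack, reported by treatment*. Keep satisfaction as a separate endpoint, as V.B already does.
2. Add a short adverse-symptom entry with onset time to the form completed at 2 hours for each attack. As II.C, item 4, shows that results exist, use the interim and end-of-study adverse-event records for data already collected, and carry the form change into any later study.
3. Attribute each event to the last bottle instilled before onset. Report frequency by treatment with exact confidence intervals, alongside the results in II.C, item 4.
4. State that end-of-study vital signs are not evidence on the acute safety of timolol.

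The cost is a slightly longer form and one extra table. The safety statement will also read less favourably: even with no events in 26 timolol exposures, the table would show a two-sided upper limit of 13.2%.

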### **B. Study Type and Design:**

B. This is a randomized, double blind, crossover, placebo-controlled, study containing a screening visit, a double-blind treatment phase, and an end-of-study visit. The participating site is the University of Kansas Medical Center where eligible subjects in the age group of 18-65 years will be enrolled. A total of 26 subjects with 1-8 migraines per month will be enrolled in a randomized double blind fashion.

Power calculations were performed and we found that twenty six subjects are required to have a 90% chance of detecting, as significant at the 5% level, an increase in the primary outcome (benefit vs. failure) from 25% in the control group to 65% in the experimental group.

C.

D. The study will consist of two visits (Visit 1 Screening/ Randomization and Visit 2 End-of-Study). Subjects will treat two of their migraine attacks with either the study drug or placebo in a double blinded, randomized, crossover fashion within a period of 8 weeks. Subjects who do not have any migraines attacks in the given 8 weeks period will be dropped from the study. Eligible

subjects will be enrolled from their usual office visits. At the Screening/ Randomization visit, subjects will provide a detailed medical and headache history, concurrent medications, demographics, a physical examination will be performed, vital signs will be obtained, a urine pregnancy test will be obtained for female subjects with child bearing potential, and verification of inclusion/exclusion criteria will be completed. Since most of the above are done as a part of the routine office visit (except for urine pregnancy screen and verification of inclusion/ exclusion criteria), collection of these data points will not be repeated.

E.

F. Subjects who meet all inclusion and exclusion criterion will be identified and recruited through routine office visits. Subjects will be randomized in a double-blinded fashion to either the study medication arm or placebo arm. They will be sent home with one bottle of the drug, which will be either the study medication (0.5% timolol ophthalmic solution) or the placebo (0.9% normal saline solution). They will be provided instructions on proper administration of the eye drops. They will treat their first migraine attack with 1 drop of ophthalmic solution in each eye (either study medication or placebo, depending upon which study arm they are in). If they miss the eye in the first attempt, they may re-administer another drop. They will be asked to then blink rapidly for 3-5 seconds to promote absorption. After 15 minutes, if the migraine headache is still present, they can re-administer one drop in each eye. They will record their migraine pain level using the comparative pain scale (Appendix B) before administering the eye drops and 2 hours after treatment. They will also report their treatment satisfaction using the forms provided (Appendix C). After the treatment of their first migraine attack, the subjects will notify the study staff and will either come in to return the first bottle and forms or they will send in their medications and forms. Once the first bottle is received, we will either mail in using a service like FedEx or they will return to pick up their second bottle. At the interim visit, if the subjects decide to return their first bottle via mail, they will be contacted by the study staff via phone call, in order to report any changes in their concomitant medications or any adverse events. The subjects will treat their second migraine attack with the second drug and again report their migraine pain level using the comparative pain scale and also report treatment satisfaction. See table below.

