### **C. Sample size, statistical methods, and power calculation**

1. A total of 26 subjects will be enrolled. Eligible subjects in the age group of 18-65 years will be enrolled at the University of Kansas Medical Center. Subjects will be randomized on 1:1 ratio. They will treat their first migraine episode with the first drug (study drug or placebo, depending upon which group they are randomized to) and then will cross over to the second drug.
2. This will be a double-blinded study. The drug bottles (study drug and placebo) will be given to the subjects in unlabeled bottles.
3. A maximum of 26 subjects will be enrolled in the study. All data collected from the subjects will be entered on a secured spreadsheet/ database. Descriptive statistics will establish baseline characteristics and adverse event frequency. Data for the primary endpoint will be statistically analyzed via 2-tailed t-test. Data for the secondary outcome measures will be statistically analyzed for both within and between group changes via 2-tailed repeated measures ANOVA and or independent or dependent t-tests as appropriate. All ANOVAs will be followed by univariate post-hoc tests.
4. Study results:  
Primary outcome change in visual analogue pain scale (VAS) 120 minutes after dose showed a similar decreases for placebo and drug with a slightly wider 95% CI for placebo. Planned secondary analysis based on satisfaction (satisfactory and very satisfactory compared to neutral and unsatisfied) was negative by Chi-square  
Post-hoc analysis was 50% or greater decrease in VAS compared to < 50% decreased was negative by chi-square

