## **D. Subject Criteria (See Vulnerable Populations appendix, if applicable):**

### **1. Inclusion criteria:**

Potential subjects must meet the following criteria at the screening visit to enter this study:

- Male or female, between the ages of 18 to 65 years
- Diagnosis of migraine, with or without aura, according to ICHD-2 criteria (Appendix A) for at least 1 year prior to screening; experience an average of 1 to 8 migraines per month.
- Females must be practicing an effective method of birth control before entry and throughout the study, or be surgically sterile, or be postmenopausal
- Females of child-bearing potential must have a negative urine pregnancy test
- Subjects should be able to demonstrate the ability to properly administer study medication
- Subjects should be able and willing to read and comprehend written instructions and complete the diary information required by the protocol
- Subjects must be capable, in the opinion of the Investigator, of providing informed consent or assent to participate in the study
- Subjects (and their legally acceptable representatives, if applicable) must provide an informed consent indicating that they understand the purpose of and procedures required for the study and are willing to participate in the study

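### The stated 90% power at 26 subjects is not assured: 26 is also the enrolment cap, incomplete pairs get no allowance, and the primary t-test is not tied to the crossover

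*Combined protocol and SAP*

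**What the plan says.** Section II.B states that "twenty six subjects are required to have a 90% chance of detecting" an increase from 25% to 65% in a benefit-or-failure outcome at the 5% level. It names no formula, sidedness or within-patient correlation. Section II.C repeats the number as a ceiling: "A maximum of 26 subjects will be enrolled in the study". Neither section adds an allowance for incomplete data.

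The design is a two-period crossover: "Subjects will treat two of their migraine attacks with either the study drug or placebo", within 8 weeks. Several rules decide whether a subject completes both periods:

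- Entry requires that subjects "experience an average of 1 to 8 migraines per month" (II.D.1).
- The second bottle follows the return of the first: "Once the first bottle is received, we will either mail in using a service like FedEx" (II.B).
- The end-of-study visit falls at 8 weeks if that comes before the visit due after the last treated attack (II.B, text after Table 1).
- Adverse effects lead to withdrawal (II.D.3 and II.L).
- "Subjects who do not have any migraines attacks in the given 8 weeks period will be dropped from the study" (II.B). Nothing is said about the analysis of a subject with exactly one treated attack.

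Section V.B makes headache severity at 120 minutes the primary endpoint. Sections II.B, II.C and V.A analyse it by a two-tailed t-test, without saying paired or independent. The choice between independent and dependent t-tests is mentioned only for secondary outcomes. Section II.C also carries results: "Primary outcome change in visual analogue pain scale (VAS) 120 minutes after dose showed a similar decreases for placebo and drug". It gives neither the number of pairs nor an interval for the within-patient difference.

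**The concern.** If 26 subjects are needed and no more than 26 may enter, any subject who does not treat two attacks takes the trial below its own requirement. The entry and timing rules make some such subjects likely. The 90% is also stated without conditions, although in a crossover with a binary outcome it depends on how strongly a patient's two responses agree.

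A second, separate gap concerns the test. A paired t-test uses the crossover but discards one-attack subjects. An independent t-test keeps them but ignores the pairing, which makes it conservative when a patient's two attacks are positively correlated.

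What is at stake is how to read a null result. Section V.B defines success by statistical significance, and section II.C already reports similar decreases with both products. A reader has to know how many pairs there were, how they were tested and what difference the result can exclude.

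**Working it through.** **1. The plan's own figure.** Inputs from II.B: 25%, 65%, 5% level, 90% power, 26 subjects. Read as 26 observations per treatment, the two-proportion formulas give:

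| Method | n per treatment for 90% | Power at 26 |
|---|---|---|
| Two-sided, unpooled variance | 28 | 88.6% |
| One-sided, pooled variance | 25 | 91.5% |
| Two-sided, pooled variance | 31 | 84.7% |

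A two-sided McNemar calculation needs 27 pairs at correlation 0.25 and 26 at 0.30. So 26 can be reached by some routes and not by others.

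**2. Dependence on the correlation, all 26 pairs complete.** McNemar normal approximation (the plan names no test for this outcome):

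power = Φ[(d√n − 1.96√p_d) / √(p_d − d²)], with d = 0.40, p_d = 0.90 − 2p₁₁ and p₁₁ = 0.65 × 0.25 + ρ√(0.65 × 0.35 × 0.25 × 0.75) = 0.1625 + 0.2065ρ.

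Example at ρ = 0.25: p₁₁ = 0.2141 and p_d = 0.4717. Then (0.4 × 5.099 − 1.96 × 0.6868) / √0.3117 = 1.24, so power is 89%. The largest possible ρ at these rates is (0.25 − 0.1625) / 0.2065 = 0.42.

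**3. Expected complete pairs.** Assumptions: Poisson attacks over 56 days, mean μ = rate × 12/365.25 × 56, and P(at least two) = 1 − e^(−μ)(1 + μ). A 7-day bottle exchange replaces 56 by 49. No adverse-event withdrawals are counted, because the documents give no rate.

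| Rate | P(two treatable attacks), no exchange / 7-day exchange |
|---|---|
| 1 per month (μ = 1.84) | 0.549 / 0.478 |
| 2 per month | 0.882 / 0.831 |
| 3 per month | 0.974 / 0.953 |
| Uniform over 1-8 | 0.953 / 0.936 |

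Expected pairs for the stated entry range: 26 × 0.953 = 24.8, or 26 × 0.936 = 24.3. About 0.9 or 1.3 subjects have exactly one treated attack.

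**4. Power at those numbers, binary outcome, formula of step 2.**

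| Pairs | ρ = 0 | ρ = 0.25 | ρ = 0.40 |
|---|---|---|---|
| 26 | 80% | 89% | 94% |
| 24.8 | 78% | 88% | 93% |
| 24.3 | 77% | 87% | 92% |

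Before rounding, the loss is 1.2 to 3.0 points. Full enumeration at 26 pairs gives 75 / 88 / 97% for exact McNemar and 82 / 92 / 99% for the uncorrected version, so the version of the test matters about as much as the attrition.

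**5. Severity t-test.** The plan gives no effect or SD. For illustration, take the effect at which a paired t-test has 90% power with 26 pairs: 0.662 SD of the within-patient difference. The paired test then has 88.5% at 24.8 pairs and 87.8% at 24.3. An independent t-test with 26 observations per product and the same effect (difference = 0.662√(2(1 − ρ)) SD), by simulation:

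| ρ | 0 | 0.20 | 0.25 | 0.30 | 0.40 | 0.50 |
|---|---|---|---|---|---|---|
| Power | 91% | 87% | 85% | 83% | 78% | 70% |
| Actual type I error | 4.9% | 2.9% | 2.4% | 2.1% | 1.3% | 0.7% |

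**6. Sensitivity.** If rates ran only from 1 to 4 per month, a range that is not in the documents, 23.2 or 22.2 pairs would be expected. Paired-t power would be 86.1% or 84.5%, and the binary loss 3-7 points. Losing six pairs leaves 20 and 80.1% for the paired t-test.

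**The case against.** The strongest reply is that the attrition limb is small. Over the stated entry range it costs 1-3 points, in a study that calls itself a pilot, and the Poisson model, uniform rates and 7-day exchange are assumptions. That stands, and it is why no case is made for a larger trial. With results in hand, the actual pairs can also be counted, and an interval then says more than a power figure. That stands too, but the unconditional 90% is still in the document and should be corrected.

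A reader might infer several stronger points that the documents do not support:

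- *That 26 is a calculation error.* Some standard formulas reach it.
- *That the unstated form of the t-test always matters more than attrition.* At correlation 0 the independent test is slightly more powerful. At 0.20 it loses about 3 points, much the same as losing two or three pairs (87.4% at 24, 85.8% at 23). At 0.25 it loses 5, similar to the low-rate scenario in step 6.
- *That the t-test choice undermines the 90% in II.B.* That figure is for a binary outcome. The severity effect used above is back-solved and is not a plan value.
- *That a 3-7 point loss is to be expected.* It rests on the 1-4 per month range.
- *That the reported null result came from an independent test.* The result summary does not say which was used.
- *That the withdrawal rules plainly conflict.* II.D.3 refers to effects of the study drug and II.L to any adverse event, but nearby wording in II.L also refers to the drug.

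**Conclusion.** The concern holds, at moderate size. The 90% is not assured, for two reasons. Fewer than 26 complete pairs should be expected under a cap equal to the requirement: about 24-25 over the stated entry range, a loss of 1-3 points, and more if the sample leans towards low attack rates. And even 26 complete pairs give anything from 80% to 94% on the McNemar approximation, depending on a within-patient correlation between 0 and 0.40 that the plan never states.

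Separately, the primary severity analysis is not tied to the crossover. This clearly outweighs the attrition only if the correlation is about 0.3-0.4 or higher, where the loss from an independent test is roughly 7-12 points, and 20 points at 0.50. The documents give no correlation, so which limb dominates cannot be settled from them. The pair counts rest on the attack model in step 3, and the t-test figures on the illustrative effect in step 5.

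**What to change.** 1. Replace the unconditional 90% with power for the number of complete pairs, shown as a range over the within-patient correlation and naming the test and its version.
2. Analyse severity at 120 minutes within patient, by a mixed model on all treated attacks: patient as random effect; treatment, period and pre-dose pain as fixed effects. Report complete pairs and one-attack subjects by sequence, and the 95% confidence interval of the within-patient difference. Show this beside the t-test, say whether that test was paired or independent, and label the model post hoc because II.C already reports results.

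The data exist, since pain is scored "before administering the eye drops and 2 hours after treatment". The cost is wording and one standard model, with no extra patients. The downsides are a less favourable stated power, a missing-at-random assumption, and little precision from one-attack subjects (a 0.9-6.5% reduction in variance over correlations 0-0.5, with a period term). The main gain is a defined rule for those subjects, use of the pairing and adjustment for period.

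As a side note, the withdrawal wording in II.D.3 and II.L should be reconciled.
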